## 8.5 Pharmacodynamic Assessments

Plasma PD samples for determination of PV and GFR will be collected at time points specified in the PK and PD Sampling Schedules ([Table 2.4](#), [Table 2.5](#), and [Table 2.6](#)). Blood sample collection, processing, and shipping details will be outlined in a separate study reference manual.

Additional PD assessments will be performed at time points specified in the Schedules of Assessments and Procedures ([Table 2.1](#), [Table 2.2](#), and [Table 2.3](#)).

### 8.5.1 Pharmacodynamic Parameters

#### 8.5.1.1 Plasma Volume

Plasma volume will be determined using FAST PV Technology for Cohorts 1 through 4.

Additionally, PV will be estimated using Nadler's formula ([Nadler et al 1962](#)) for Cohorts 1 through 4. Nadler's formula ([Nadler et al 1962](#)) is as follows:

$$\text{Plasma Volume (males)} = 0.3669 \times (\text{Height [m]})^3 + 0.03219 \times (\text{Body Weight [kg]}) + 0.6041$$

$$\text{Plasma Volume (females)} = 0.3561 \times (\text{Height [m]})^3 + 0.03308 \times (\text{Body Weight [kg]}) + 0.1833$$

#### 8.5.1.2 Glomerular Filtration Rate

Measured GFR will be determined using FAST mGFR Technology for Cohorts 1 through 4.

Glomerular filtration rate will also be determined using the Iohexol clearance test, a widely accepted research gold standard for measuring GFR in patients with stable renal function, for Cohorts 2 through 4. Plasma concentrations of Iohexol will be determined using a validated high performance liquid chromatography assay.

Additionally, eGFR will be calculated using the MDRD ([Levey et al 1999](#)), CKD-EPI ([Levey et al 2009](#)) and Cockcroft-Gault ([Cockcroft et al 1976](#)) equations for Cohorts 1 through 4.

CONFIDENTIAL

The MDRD equation (Levey et al 1999) is as follows:

$$\text{GFR (mL/min/1.73 m}^2\text{)} = 175 \times (\text{S}_{\text{cr}})^{-1.154} \times (\text{Age})^{-0.203} \times (0.742 \text{ if female}) \times (1.212 \text{ if African American})$$

The CKD-EPI equation (Levey et al 2009) for eGFR for specified race, sex, and  $\text{S}_{\text{cr}}$  in mg/dL and  $\mu\text{mol/L}$  is presented in Table 8.1 and Table 8.2, respectively.

The Cockcroft-Gault equation (Botev et al 2009) is as follows:

$$\text{GFR} = [(140-\text{Age}) \times (\text{Weight}) \times 0.85 \text{ if female}] / 72 \times \text{S}_{\text{Cr}}$$

**Table 8.1 Chronic Kidney Disease Epidemiology Collaboration Equation for Estimating Glomerular Filtration Rate Expressed for Specified Race, Sex, and Serum Creatinine (mg/dL)**

Race	Sex	$\text{S}_{\text{cr}}$ (mg/dL)	Equation (age in years for $\geq 18$ )
Black	Female	$\leq 0.7$	$\text{GFR} = 166 \times (\text{S}_{\text{cr}}/0.7)^{-0.329} \times (0.993)^{\text{Age}}$
Black	Female	$> 0.7$	$\text{GFR} = 166 \times (\text{S}_{\text{cr}}/0.7)^{-1.209} \times (0.993)^{\text{Age}}$
Black	Male	$\leq 0.9$	$\text{GFR} = 163 \times (\text{S}_{\text{cr}}/0.9)^{-0.411} \times (0.993)^{\text{Age}}$
Black	Male	$> 0.9$	$\text{GFR} = 163 \times (\text{S}_{\text{cr}}/0.9)^{-1.209} \times (0.993)^{\text{Age}}$
White or other	Female	$\leq 0.7$	$\text{GFR} = 144 \times (\text{S}_{\text{cr}}/0.7)^{-0.329} \times (0.993)^{\text{Age}}$
White or other	Female	$> 0.7$	$\text{GFR} = 144 \times (\text{S}_{\text{cr}}/0.7)^{-1.209} \times (0.993)^{\text{Age}}$
White or other	Male	$\leq 0.9$	$\text{GFR} = 141 \times (\text{S}_{\text{cr}}/0.9)^{-0.411} \times (0.993)^{\text{Age}}$
White or other	Male	$> 0.9$	$\text{GFR} = 141 \times (\text{S}_{\text{cr}}/0.9)^{-1.209} \times (0.993)^{\text{Age}}$

Source: National Institute of Diabetes and Digestive and Kidney Diseases, Estimating Glomerular Filtration Rate (2015)

**Table 8.2 Chronic Kidney Disease Epidemiology Collaboration Equation for Estimating Glomerular Filtration Rate Expressed for Specified Race, Sex, and Serum Creatinine ( $\mu\text{mol/L}$ )**

Race	Sex	$\text{S}_{\text{cr}}$ ( $\mu\text{mol/L}$ )	Equation (age in years for $\geq 18$ )
Black	Female	$\leq 61.9$	$\text{GFR} = 166 \times (\text{S}_{\text{cr}}/61.9)^{-0.329} \times (0.993)^{\text{Age}}$
Black	Female	$> 61.9$	$\text{GFR} = 166 \times (\text{S}_{\text{cr}}/61.9)^{-1.209} \times (0.993)^{\text{Age}}$
Black	Male	$\leq 79.6$	$\text{GFR} = 163 \times (\text{S}_{\text{cr}}/79.6)^{-0.411} \times (0.993)^{\text{Age}}$
Black	Male	$> 79.6$	$\text{GFR} = 163 \times (\text{S}_{\text{cr}}/79.6)^{-1.209} \times (0.993)^{\text{Age}}$
White or other	Female	$\leq 61.9$	$\text{GFR} = 144 \times (\text{S}_{\text{cr}}/61.9)^{-0.329} \times (0.993)^{\text{Age}}$
White or other	Female	$> 61.9$	$\text{GFR} = 144 \times (\text{S}_{\text{cr}}/61.9)^{-1.209} \times (0.993)^{\text{Age}}$
White or other	Male	$\leq 79.6$	$\text{GFR} = 141 \times (\text{S}_{\text{cr}}/79.6)^{-0.411} \times (0.993)^{\text{Age}}$
White or other	Male	$> 79.6$	$\text{GFR} = 141 \times (\text{S}_{\text{cr}}/79.6)^{-1.209} \times (0.993)^{\text{Age}}$

Source: National Institute of Diabetes and Digestive and Kidney Diseases, Estimating Glomerular Filtration Rate (2015)

CONFIDENTIAL

## 8.6 Safety Assessments

### 8.6.1 Adverse Events

Subjects will be monitored for AEs from administration of the first dose of study drug through the EOS visit. Refer to [Section 9](#) for additional details.

### 8.6.2 Clinical Laboratory Tests

A certified laboratory will be utilized to process and provide results for the clinical laboratory tests listed in [Table 8.3](#). The baseline laboratory test results for clinical assessment for a particular test will be defined as the last measurement prior to the initial dose of study drug.

During the screening period, if a subject has an out-of-range value for a clinical laboratory parameter which the investigator believes is not clinically significant, but the investigator wants to confirm with a repeat laboratory test, a single repeat is allowed to confirm the initial result.

**Table 8.3 Clinical Laboratory Tests**

Hematology	Coagulation	Serum Chemistry	Urinalysis a,b,e
Hematocrit	INR c	Sodium	Nitrites
Hemoglobin		Potassium	Leukocytes
Red blood cell count		Chloride	Protein
Mean corpuscular volume		Albumin	Glucose
White blood cell count		Aspartate aminotransferase	Ketones
Platelet count (estimate not acceptable)		Alanine aminotransferase	Urobilinogen
Neutrophils (absolute)		Alkaline phosphatase	Bilirubin
Eosinophils (absolute)		Creatine phosphokinase	Blood
Basophils (absolute)		Glucose d	pH
Lymphocytes (absolute)		Total cholesterol d	Specific gravity
Monocytes (absolute)		BUN	
		Creatinine	
		Total bilirubin	
		Calcium	
		Total protein	
		Phosphorous	

- a. In case of clinically significant findings, a microscopic analysis will be performed.
- b. If 1+ or greater protein is noted in the urinalysis, a calculated urine protein to creatinine ratio will be performed.
- c. Cohorts 3 and 4 only.
- d. Should be collected after fasting for a minimum of 8 hours.
- e. A urine protein to creatinine ratio will be performed only at predose on testing day and 24 hours postdose. Subjects will be fasting prior to this measurement.

For any laboratory test value outside the reference range that the investigator considers clinically significant during the on-study period (ie, following dose administration), the investigator will:

- Repeat the test to verify the out-of-range value and clinical significance.

CONFIDENTIAL

- Follow the out-of-range value to a satisfactory clinical resolution.
- Record as an AE any laboratory test value that (1) is confirmed by repeat and the investigator considers clinically significant, (2) requires a subject to be discontinued from the study, (3) requires a subject to receive treatment, or (4) requires a change or discontinuation of the study drug (if applicable).

#### 8.6.3 Other Tests

The following tests will be performed:

- Urine drugs of abuse (at a minimum, cocaine, cannabinoids, amphetamines, opiates, barbiturates, benzodiazepines, and phencyclidine [ICON site only] and serum alcohol screens
- Serology tests (ie, HIV-1 and HIV-2 antibodies, HBsAg, and HCV antibody)
- Follicle-stimulating hormone (females only; as needed to confirm postmenopausal status)
- Pregnancy Test (females only)

During the screening period, urine drugs of abuse and serum alcohol screens may not be repeated for eligibility.

#### 8.6.4 Vital Signs

Vital signs assessments will include oral temperature (°C), respiratory rate (breaths per minute), systolic and diastolic BP (mmHg) and pulse rate (bpm). Blood pressure and pulse rate will be measured after the subject has been resting quietly in a supine position or in the most recumbent position possible for at least 5 minutes.

Vital signs abnormalities that (1) are considered clinically significant initially and on confirmation, (2) require a subject to be discontinued from the study, (3) require a subject to receive treatment, or (4) require a change or discontinuation from the study drug (if applicable) will be recorded as AEs.

#### 8.6.5 Pulse Oximetry

Oxygen saturation will be measured by pulse oximetry.

Oxygen saturation abnormalities that (1) are considered clinically significant initially and on confirmation, (2) require a subject to be discontinued from the study, (3) require a subject to receive treatment, or (4) require a change or discontinuation from the study drug (if applicable) will be recorded as AEs.

#### 8.6.6 Physical Examination

Complete physical examinations (including eyes, ears, nose and throat, cardiac, peripheral vascular, pulmonary, musculoskeletal, neurologic, abdominal, lymphatic, and dermatologic systems) will be performed, and abnormal findings will be carefully documented in the subject's eCRF.

CONFIDENTIAL

An abnormal physical examination finding that is considered clinically significant and (1) requires the subject to be discontinued from the study, (2) requires the subject to receive treatment, or (3) requires a change or discontinuation of the study drug (if applicable) will be recorded as an AE.

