### **3.4        Summary of Findings to Date**

#### **3.4.1      Nonclinical Studies**

Proof-of-concept nonclinical pharmacology studies have been conducted in dogs to confirm the assessment of GFR using the FAST mGFR TestTM ([Wang 2011](#)). The results of these studies provide evidence that the method, in combination with the VFI, provides an accurate GFR.

The liquid VFI agent (FD004) was evaluated in a full range of nonclinical studies, including pharmacology, safety pharmacology, pharmacokinetic (PK), single-dose toxicity, genotoxicity, and immunotoxicity in male and female rats and dogs at concentrations from 16 (FD003) to 26 (FD001) fold greater than the planned maximum human dose based upon observed and predicted area under the concentration-time curve (AUC) values. For more information please refer to the current Investigator's Brochure.

CONFIDENTIAL

Observed effects of the VFI (FD001 and FD003) in pivotal single dose animal studies at higher doses (ranging from approximately 62 to approximately 100 times the planned human clinical dose of 47 mg [29 mg/m^2]) included emesis in dogs, discolored urine, and a species specific effect (rats not dogs) on tissue macrophages of the lymph nodes and spleen resulting in cell death, which did not reverse during the recovery period. The clinical relevance of the macrophage finding in rats is unknown.

Though the VFI has shown no pharmacological activity at the human dose in receptor screening, a cytochrome P450 (CYP) inhibition study has been performed to assess potential for interaction with concomitant medications. The ability of FD001 and FD003 to inhibit CYP isoforms, CYP1A2, CYP2B6, CYP2C8, CYP2C9, CYP2C19, CYP2D6, and CYP3A4/5, was assessed to identify the potential of drug-drug interactions. FD001 and FD003 were each preincubated for 0 or 30 minutes at 7 concentrations (0.1, 0.3, 1, 3, 10, 30, and 100  $\mu$ M) with human liver microsomes in the presence of probe substrates phenacetin, efavirenz, amodiaquine, diclofenac, mephenytoin, dextromethorphan, midazolam, and testosterone to determine if there was a direct effect on CYP1A2, CYP2B6, CYP2C8, CYP2C9, CYP2C19, CYP2D6, and CYP3A4/5, respectively. Additionally, FD001 and FD003 were each incubated in the presence of dihydronicotinamide-adenine dinucleotide phosphate (NADPH) for up to 30 minutes at 37°C to assess the time-dependent inhibitory effects on CYP enzymes.

Results from the CYP inhibition studies suggest that:

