#### 8.6.7      Electrocardiograms

Subjects must be resting quietly in a supine position or in the most recumbent position possible for at least 5 minutes before the ECG is obtained. The following ECG parameters will be recorded: HR, RR, PR, QRS, and QT and QT interval corrected for HR using Fridericia's formula (QTcF) intervals.

Electrocardiogram assessment will include interpretation of the tracings, eg, rhythm, presence of arrhythmia or conduction defects, morphology, any evidence of myocardial infarction, or ST segment, T-wave, and U-wave abnormalities. The investigator or designee is responsible for reviewing and over-reading the ECG interpretation, for assessing whether the ECG machine interpretation findings are accurate, appropriate, normal or abnormal, and for providing corrected interpretations as appropriate. In addition, any abnormal ECGs will be assessed for clinical significance.

Additional ECGs may be obtained if clinically indicated. Any additional relevant data obtained by the investigator during the course of this study will be supplied to the sponsor.

For any ECG that the investigator considers clinically significant, the investigator will:

- Repeat the ECG.
- Follow-up ECG(s) will be obtained if any significant abnormalities are detected after dose administration to document resolution and as clinically indicated.
- Record as an AE any ECG that (1) is confirmed and the investigator considers clinically significant, (2) requires a subject to be discontinued from the study, (3) requires a subject to receive treatment, or (4) requires a change or discontinuation of the study drug (if applicable).

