## **9 ADVERSE EVENTS**

An AE is defined as any untoward medical occurrence in a subject administered a pharmaceutical product during the course of a clinical investigation. An AE can therefore be any unfavorable and unintended sign, symptom, or disease temporally associated with the use of an investigational product, whether or not thought to be related to the investigational product.

Subjects will be monitored throughout the study for AEs, from administration of the first dose of study drug through the EOS visit. Adverse events that are identified at the last assessment visit (or the early termination visit) as specified in the protocol must be recorded on the AE eCRF with the status of the AE noted. All events that are ongoing at this time will be recorded as ongoing on the eCRF. All (both serious and nonserious) AEs must be followed until they are resolved or stabilized, or until attempts to determine resolution of the event are exhausted. The investigator should use his/her discretion in ordering additional tests as necessary to monitor the resolution of such events.

The procedures specified in [Section 9.4](#) are to be followed for reporting SAEs.

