### 9.2.2 Intensity

The intensity of an AE will be graded according to the following definitions:

- Mild: Any symptom of which the subject is aware, but which is easily tolerated; asymptomatic or mild symptoms; clinical or diagnostic observations only; intervention not indicated.
- Moderate: Any symptom which is discomforting enough to cause interference with a subject's usual activity; minimal, local, or noninvasive intervention indicated; limiting age-appropriate instrumental activities of daily living (ADL).
- Severe: Any symptom which causes a subject's inability to perform usual activity; severe or medically significant but not immediately life-threatening; hospitalization or prolongation of hospitalization indicated; disabling; limiting self-care ADL.

CONFIDENTIAL

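### The physical-examination rule asks for clinical significance plus an action before a finding is recorded as an AE, which conflicts with Section 9 and with the rules for laboratory tests, vital signs, oximetry and ECG

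*Protocol*

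**What the plan says.** Protocol 8.6.6 opens its rule with "An abnormal physical examination finding that is considered clinically significant and (1) requires the subject to be discontinued from the study", gives treatment as the second condition, and closes with "3) requires a change or discontinuation of the study drug (if applicable) will be recorded as an AE". Clinical significance stands outside the numbered list. The word 'or' joins only the three actions. SAP 6.2.5 repeats the sentence. Section 8.6.6 also says that "abnormal findings will be carefully documented in the subject's eCRF".

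The other objective safety assessments put clinical significance inside the list, as item (1):
- Vital signs (8.6.4): "Vital signs abnormalities that (1) are considered clinically significant initially and on confirmation, (2) require a subject to be discontinued from the study", followed by treatment or a drug change as further alternatives. Pulse oximetry (8.6.5) has the same structure.
- ECG (8.6.7): "Record as an AE any ECG that (1) is confirmed and the investigator considers clinically significant", with the three actions as alternatives. The laboratory rule in 8.6.2 is built the same way and asks for confirmation by repeat.

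The general definition in Section 9 has no action condition: "An AE can therefore be any unfavorable and unintended sign, symptom, or disease temporally associated with the use of an investigational product". Section 9.1 accepts none as the action taken. The Mild grade in 9.2.2 includes "clinical or diagnostic observations only; intervention not indicated".

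**The concern.** AEs and physical-examination findings are both primary safety endpoints (Protocol 10.3.1.1). Examination findings are only listed (Protocol 10.6, SAP 10.1.11.6). The AE page is thus their only route into a summary table. If a site reads 8.6.6 as the specific instruction for examinations, a new finding that the investigator calls clinically significant but that leads to no action goes no further than the eCRF and the listing. The same judgement about a confirmed blood pressure or ECG abnormality would produce an AE.

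Consistency between sites is also at stake. The protocol synopsis places Cohorts 1 and 2 at one unit, Cohort 4 at the other, and Cohort 3 at both. TEAEs are tabulated by cohort. If one unit follows 8.6.6 and the other follows Section 9, a difference in recording could look like a difference by renal function.

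**Working it through.** The plan gives no figure on this point, so the check is logical. For each abnormality let S mean that it is judged clinically significant (and confirmed, where the rule asks for that), D that it requires discontinuation from the study, T that it requires treatment, and C that it requires a change or stop of study drug.

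| Source | Rule for recording an AE |
|---|---|
| Protocol 8.6.6, SAP 6.2.5 (physical examination) | S and (D or T or C) |
| Protocol 8.6.4, 8.6.5 (vital signs, oximetry) | S or D or T or C |
| Protocol 8.6.2, 8.6.7 (laboratory, ECG), numbered list alone | S or D or T or C |
| Protocol 8.6.2, 8.6.7, with their lead-in, which already limits the steps to significant results | S and (S or D or T or C), which reduces to S |
| Protocol Section 9 | any unfavourable, unintended sign; no action term |

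**Counting the combinations.** Four yes/no conditions give 2^4 = 16 combinations.
- Physical examination: S = 1 leaves 2^3 = 8 combinations. The one with no action fails, so 8 − 1 = 7 are recorded.
- Numbered list alone: only the all-zero combination fails, so 16 − 1 = 15 are recorded. This differs from the examination rule in 15 − 7 = 8 combinations. One is S = 1 with D = T = C = 0. The other seven have S = 0 and at least one action (2^3 − 1 = 7).
- Laboratory and ECG rules with the lead-in: 8 are recorded. This differs from the examination rule in 8 − 7 = 1 combination, again S = 1 with D = T = C = 0.

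The seven combinations with S = 0 depend on how the laboratory and ECG text is read, so nothing is rested on them. The combination with significance and no action is in conflict on either reading. Section 9 also covers it when the sign is new after dosing. These are logical cases; they say nothing about how often each would occur.

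**Following that case to the outputs.** Under 8.6.6 taken alone, the finding is entered in the eCRF and printed in SAP Listing 16.2.8.5. It is absent from SAP Tables 14.3.1.1 to 14.3.1.4, which count TEAEs. Under Section 9 it is in both places.

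**After the change proposed below.** For a new or worsened finding the rule becomes S or D or T or C. It then records 15 of 16 combinations, and the disputed case moves from not recorded to recorded.

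**The case against.** The strongest reply is that 8.6.6 says which findings will be recorded and never says only those. Section 8.6.1 refers sites to Section 9 for AEs, and a site that reads the whole protocol would record the finding. This stands: a reader might infer that untreated findings are barred from the AE page, and the text does not support that. Nor are the data lost, since the eCRF and the listing keep them and the safety review committee looks at safety data generally (Protocol 5.1.1). What remains is that a specific sentence and a general one point different ways, with no statement of which governs.

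Three further inferences are tempting and should not be drawn.
- **Two of the three action conditions are inert in the single-dose cohorts.** A drug change has little scope after the only dose, but the first condition concerns leaving the study. Subjects stay in the study to about Day 21 and can be withdrawn for safety (Protocol 6.3, 9.3).
- **The cohort stopping rule is weakened.** The AE-count criterion in Protocol 6.4.1 counts treatment-related moderate or severe events. Findings that need no intervention would mostly be graded Mild and would not count even if recorded.
- **The rule hides the animal signal.** Protocol 3.4.1 reports an effect on "tissue macrophages of the lymph nodes and spleen resulting in cell death, which did not reverse during the recovery period". It was seen in rats and not dogs, at about 62 to 100 times the planned human dose, and nothing in the documents says that it could be detected on examination. Dextran allergy is described as acute (Protocol 3.6.2). AE collection runs across all postdose time points, so it would usually catch a reaction before a scheduled examination did.

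It is also fair to note that the four comparison rules require confirmation before significance alone is enough. Section 8.6.6 is therefore not one word away from them.

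**Conclusion.** The inconsistency is real and limited. The rule in Protocol 8.6.6 and SAP 6.2.5 conflicts with the protocol's own AE definition, with its action and intensity categories, and with four parallel rules. No reason is given for the difference. Compared with Section 9, following 8.6.6 can only lower the AE count.

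The number of findings affected cannot be estimated: it depends on how many clinically significant findings need no action and on how each site resolves the conflict. The conclusion assumes that at least one site may treat the specific sentence as controlling. If both sites apply Section 9 throughout, no AE is lost. The point merits correction because it touches a primary endpoint and is cheap to settle; it does not call the study's safety data as a whole into question.

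**What to change.** Reword Protocol 8.6.6 and SAP 6.2.5 along these lines: a physical-examination finding that is new or worsened since baseline will be recorded as an AE if it (1) is considered clinically significant, (2) requires discontinuation from the study, (3) requires treatment, or (4) requires a change or discontinuation of study drug.

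This should be presented as alignment with Section 9. It is not a copy of the vital-sign, oximetry and ECG rules, because it has no confirmation step and adds the baseline qualifier. The qualifier avoids recording stable findings that inclusion criterion 12 allows at entry in Cohorts 3 and 4.

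The cost is one sentence in each document and a few more AEs, mostly mild. Only AE recording changes; dosing and clinical management are untouched.
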